This intervention study will examine whether there is an indication that targeted clearing of fibrin and the resulting leukocytes from the alveolar space early in the progression of COVID-19, would have a protective effect on inflammation, facilitating the restoration of alveolar-capillary barrier and survival. The trial, through accelerated clearance, has the potential to decrease the need for ventilatory support, decreased length of ICU stay and decreased mortality.

## 2.4 Rationale for rtPA dose – Cohort 1

Rehberg et al. USA (Rehberg et al. 2014) in a sheep model of lung injury post burn and smoke inhalation injury randomly assigned sheep to intravenous saline plus saline nebulization (control), intravenous recombinant human antithrombin (AT, 6 IU/kg/h) started 1 hour after injury plus saline nebulization or intravenous AT combined with nebulized heparin (10,000 IU every 4 hours, started 2 hours after injury), and nebulized tissue plasminogen activator (2 mg every 4 hours, started 4 hours after injury, a total of 22mg) (triple therapy, n = 6 each) with animals mechanically ventilated and fluid resuscitated according to standard protocols during the 48-hour study period. Triple therapy resulted in improved  $\text{PaO}_2/\text{FiO}_2$

ratio ( $p = 0.007$ ), attenuated pulmonary obstruction ( $p = 0.02$ ) and shunting ( $p = 0.025$ ), as well as reduced ventilatory pressures versus AT i.v. at 48 hours.

Hofstra et al, Netherlands (Hofstra et al. 2013) in a rat model of bacterial infection administered nebulised rtPA (1.25 mg/kg, prophylactically and at 6 and 12 h). Nebulized rtPA enhanced the bronchoalveolar fibrinolytic system, as reflected by a significant reduction of PAI-1 activity levels in bronchoalveolar lavage fluid, and a consequent increase in plasminogen activator activity (PAA) levels to supranormal levels and both treatments also significantly affected systemic fibrinolysis as reflected by a significant increase in PAA levels in plasma to supranormal levels. Neither nebulized rtPA nor anti-PA1-1 affected pulmonary inflammation as evaluated by the neutrophil and mononuclear cell count.

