## 2.6 Assessment and management of risk

Deposition and removal of fibrin are critical processes in reducing blood loss, wound healing and repair. Thrombin is the final enzyme of the coagulation cascade and converts soluble fibrinogen into a fibrin meshwork that traps red cells and other cellular debris. The removal of the fibrin meshwork occurs via fibrinolysis that requires plasmin generated from zymogen plasminogen that normally circulates in plasma and is incorporated into the clot at the time of formation. Plasminogen is activated by two proteases: urokinase-type plasminogen activator (uPA) or tissue plasminogen activator (tPA), both of which are primarily synthesized by the endothelium (Weisel and Litvinov 2014). Fibrinolysis is tightly regulated under normal physiological conditions. The catalytic activities of tPA and uPA are curtailed through the inhibitory proteins plasminogen activator inhibitor-1 (PAI-1) and  $\alpha_2$ -antiplasmin which inhibits free tPA but not that bound to a fibrin clot. Finally, circulating tPA has a very short half-life of 5–8 min (Sheehan and Tsirka 2005).

Recombinant tPA (rtPA, alteplase) is licensed for the thrombolytic treatment of acute myocardial infarction, massive pulmonary embolism with haemodynamic instability and acute ischaemic stroke. The dosages used in these conditions are typically around 0.9 to 1.2 mg/Kg administered over 1 to 2 hrs (Alteplase June 2019). rtPA administered by the normal intravenous route carries a risk of bleeding and the extent of this risk is related to the drug dose (Lee et al. 2015). The highest number of bleeding events were seen in trials involving acute ischemic stroke where the reported complications were symptomatic intracranial haemorrhage (6%), other major haemorrhage (2%), and angioedema (5%) (Miller, Simpson, and Silver 2011). Angioedema is related to the rapid generation of bradykinin from high-molecular-weight kininogen by plasmin (Fugate, Kalimullah, and Wijdicks 2012). The risk factors for symptomatic intracranial haemorrhage include age, male gender, obesity, increased stroke severity, diabetes, hyperglycemia, uncontrolled hypertension, combination antiplatelet use, large areas of early ischemic change, atrial fibrillation, congestive heart failure, and leukoaraiosis. A risk factor for angioedema is the use of angiotensin-converting enzyme inhibitor.

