The potential for pulmonary haemorrhage has been carefully considered during the study design. This risk is probably related to the generation of plasmin in the alveoli, responsible for the fibrinolysis. To date no bleeding has been seen in anecdotal reports using 1 to 2mg/Kg of nebulised rtPA per day, over 3 - 14 days in patients with plastic bronchitis. Plasmin generation, in addition to the amount of rtPA inhaled, is also related to the availability of plasminogen in the alveoli, which is limited by the amount that can cross the alveolar capillary barrier. Indeed this limited availability has the potential to result in therapeutic failure. The other factor that may contribute to the bleeding is the use of therapeutic anticoagulation. Concurrent therapeutic anticoagulation is common with the use of rtPA as it prevents recurrence of thrombosis. There is emerging evidence that these patients have pulmonary thrombin at the segmental and sub segmental, and importantly they appear to a very strong prothrombotic tendency. It is important to note that the bleeding risk in the literature typically includes the concurrent use of anticoagulants. A strong prothrombotic tendency can result in relative resistance to the action of anticoagulants. Indeed patients presenting with elevated troponin in our organisation have been noted to have atypical coronary thrombosis with regards extent and clot burden .

We hypothesise that this risk will be much reduced if administered by inhalation. This is because relatively little of the drug is expected to cross the alveolar-capillary interface and enter the bloodstream. The doses being used in this study are lower than that used in studies for myocardial infarction and stroke and similar to that used in venous thrombosis. Additionally, as the absorption rate is slow, the rapid inactivation of rtPA in the circulation will prevent accumulation to the level normally associated with bleeding. The background risk of pulmonary bleeding in COVID-19 pneumonia is low, with this symptom reported in only 5% of cases (Huang et al. 2020). The bleeding risk is accurately predicted from the plasma fibrinogen level which provides a measure of the rtPA absorbed. This will be monitored and if plasma fibrinogen levels fall to <1.0 g/L, the further dosing of rtPA in that patient will be stopped. Replacement therapy, either in the form of fibrinogen concentrate or cryoprecipitate will be administered to return fibrinogen to >1.0 g/L.

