The table below summarises the risks, frequencies and mitigations of the IMP(s) and NIMP(s):

Name of IMP(s)	Potential risk	Risk Frequency	Risk Management
rtPA (alteplase)	Pulmonary haemorrhage	Uncommon when administered intravenously, unknown when administered by ventilation	Stop rtPA nebulisation for this patient, and administer fibrinogen concentrate or cryoprecipitate if fibrinogen is < 1.0 g/L, and other supportive treatment including IV tranexamic acid. May trigger stopping rule for trial if considered a

			major bleed by ISTH criteria (see section 7.10)
rtPA (alteplase)	Minor bleeding particularly traumatic – suction through endotracheal tube or at site of venepuncture	Common when administered intravenously, unknown when administered by ventilation	Supportive treatment, and use caution during suction
rtPA (alteplase)	hypersensitivity reactions (e.g. rash, urticaria, bronchospasm, angio-oedema, hypotension, shock)*	Rare when administered intravenously, unknown when administered by ventilation	Anti- allergic medications
rtPA (alteplase)	serious anaphylaxis	very rare when administered intravenously, unknown when administered by ventilation	Treat per local protocols and stop further administration of rtPA for this patient.
rtPA (alteplase)	Major Bleeding including intracerebral haemorrhage	Common when administered intravenously, unknown when administered by ventilation.	Rapid absorption is required to achieve high enough levels to result in bleeding. the plasma half-life is 5 minutes.  Stop rtPA nebulisation for that patient, and administer fibrinogen concentrate or cryoprecipitate if fibrinogen is < 1.0 g/L. May trigger stopping rule for trial (see section 7.10)

The table below summarise the risks and mitigations of all test above standard care that are being performed in a table:

Intervention	Potential risk	Risk Management
Additional blood samples	Related to venepuncture, which is done as standard of care.	Press on the site of blood tests

## 2.7 Safety data from cohort 1

Preliminary data from the 9 treatment arm patients is summarised below (this data is preliminary data and is not the final analysis):

All bleed events were identified as adverse events of special interest and evaluated for severity (mild, moderate and severe as described in section 8.3.1) and causality. In addition, the ISTH (International Society of Haemostasis and Thrombosis) classification for bleed severity as used for anticoagulation studies was implemented.

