### 2.7.4 Exploratory biomarkers for fibrinolytic pathway

The plasma fibrinolytic pathway was evaluated through measurement of plasminogen, the precursor of plasmin and the alpha-2 antiplasmin its major inhibitor, and these were within normal limits.

Preliminary analysis of the tPA data show no changes were seen during tPA administration. Similarly, no changes in concentration of tPA antigen, PAI-1 antigen and tPA-PAI-1 complexes were seen. The abnormalities were consistent with COVID -19 with no evidence of any significant absorption of tPA or activation of the fibrinolytic pathway.

	baseline		day 3		day 5		day 13	
	Median	10% - 90%	Median	10% - 90%	Median	10% - 90%	Median	10% - 90%
No. of patients	9		9		8		2	
Plasminogen activity IU/dL	108	63.5 - 124.7	111	36.2 - 127.8	97.5	76.5 - 130	70 - 112	
Alpha 2 antiplasmin IU/dL	112.5	103.6 - 129 .4	116	104.6 - 128	119	106.1 - 139	112 - 116	
PAI -1 antigen ng/mL	41	31.6 - 58.4	39	28 - 54.2	38	26.8 - 92.2	25 - 35	
tPA antigen ng/mL	16.5	7.8 - 37.2	14	9 - 23	14	11.1 - 40	26 - 10	

In accordance with the MRC/DH/MHRA Joint Project Risk-adapted Approaches to the Management of Clinical Trials of Investigational Medicinal Products, this trial is categorised as:

- Type B = Somewhat higher than the risk of standard medical care

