### 7.3 Treatment Schedule for nebulisation

Patients in the rtPA and SOC group will receive the first dose as soon as possible after enrolment, and in accordance with the dosing schedule below. The time of initiation of the first dose will be recorded and the timing of the initiation of subsequent doses will be relative to this time. 10mg rtPA will be administered by nebulisation every 6 hours. Treatment with rtPA will be administered at a dose of 10 mg every 6hrs for a minimum of 5 days initially and a maximum of 14 treatment days overall.

#### 7.3.1 Cohort 1

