## 7.5 Visit schedule and assessments post initiation of treatment

### 7.5.1 Cohort 1 and 2

Any assessments that are done as per routine care do not need to be repeated.

- Documentation of respiratory status: Respiratory status of patients is monitored hourly and data points will be extracted for every four hours where available until 5 days after the last dose for cohort 1, but one data point per day is required as a minimum. For cohort 2 data will be extracted once a day coinciding with the worst PF ratio. As PF ratio is the primary endpoint, in addition to the worst PF ratio over the preceding 24 hrs up to a maximum of 6 data points spread across 24 hrs that represents patients clinical status will be extracted. Similar to cohort 1 respiratory data will be collected until 5 days after the last dose. After this period, respiratory status is to be documented weekly (+/- 1 day) until discharge, death, or 28 days whichever occurs first. The time of measurement should be documented.
- The variables include:
  - Details of oxygen and respiratory support including the type of device, FiO2 Respiratory rate
  - PaO2
  - For IMV patients, details of ventilation including but not exclusively the below
    - Tidal volume (in mL)
    - Full sedation or not – not for cohort 2
    - Paralysis or not – not for cohort 2.
    - Patient position – not for cohort 2
    - Peak inspiratory pressure (collected for computing compliance)
    - PEEP (collected for computing compliance)
  - For non-invasive oxygen support patients:
    - National Early Warning Score (NEWS 2) – not for cohort 2
    - Oxygen flow rate
    - SpO2
  - For CPAP patients
    - Positive end expiry pressure (PEEP)

The following tests are to be done at a minimum once a day until 5 days after the last dose (day 7 for SOC patients) in cohort 1, a minimum every other day in cohort 2, and then as required until day 28, discharge or death whichever occurs first.

- Local blood testing as per section 7.6.2

The following tests will be done once at 48 h (+/- 24 h) and 96 h (+/- 24h) after start of treatment and then twice weekly while on treatment until 5 days after stopping treatment. After this period, testing should be weekly (+/- 1 day) until day 28, discharge or death whichever occurs first. Twice weekly testing should be evenly spaced across weekdays if possible.

- Research blood sampling as per section 7.6.2

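### Research samples are not tied to a nebulisation, so with a tPA half-life of 5–8 minutes the untimed tPA antigen results cannot by themselves exclude transient absorption

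*Protocol*

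**What the plan says.** Section 2.6 of the protocol expects low systemic exposure: "relatively little of the drug is expected to cross the alveolar-capillary interface and enter the bloodstream". It calls absorption slow, without giving a rate. It gives the half-life twice: "circulating tPA has a very short half-life of 5–8 min" in the text and "the plasma half-life is 5 minutes" in the risk table.

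Section 7.5.1 sets the research sampling: "The following tests will be done once at 48 h (+/- 24 h) and 96 h (+/- 24h) after start of treatment", then twice weekly. For the later draws it adds: "Twice weekly testing should be evenly spaced across weekdays if possible". Footnote c of Appendix 1 repeats this. Neither place relates a draw to a dose or asks for the time since the last nebulisation.

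Section 2.7.4 reports preliminary cohort 1 results for tPA antigen, PAI-1 antigen, tPA-PAI-1 complexes, plasminogen and alpha-2 antiplasmin. It concludes that there was "no evidence of any significant absorption of tPA or activation of the fibrinolytic pathway".

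**The concern.** The statement in 2.7.4 makes two claims: that little tPA was absorbed, and that the fibrinolytic pathway was not activated. Of the markers listed, tPA antigen bears most directly on the first. A marker cleared within minutes shows a brief pulse only if blood is drawn within minutes of it, and this schedule leaves that to chance.

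The protocol's own background keeps absorption an open question. The rat study in section 2.4 reported "a significant increase in PAA levels in plasma to supranormal levels" after nebulised rtPA. The risk table in 2.6 says bleeding would require rapid absorption, and 2.6 also links haemorrhage to peak rtPA levels. The untimed samples are therefore least informative in the scenario that the protocol itself treats as the hazardous one.

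Cohort 2 keeps the same research sampling with a 20 mg single dose instead of 10 mg and longer dose intervals. Minimum local blood testing, which includes fibrinogen, goes from daily to every other day.

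**Working it through.** The documents give no sampling-coverage figure, so there is nothing to reproduce.

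**Inputs.** Half-life 5–8 min (2.6). Dose interval 360 min in cohort 1 (7.3: "10mg rtPA will be administered by nebulisation every 6 hours"). In cohort 2 it is 480 min for IMV, and 720 min for non-invasive support after the first two days (7.3.2). Assumptions not in the documents: the stated half-life applies to tPA antigen as measured; a sample counts as informative while tPA is above 10% of peak; and draws fall at random within the dose interval.

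**Step 1: how uncontrolled the timing is.** A window of 24 h either way is 48 h wide. It spans 48/6 = 8 dose intervals at 6-hourly dosing, 48/8 = 6 at 8-hourly and 48/12 = 4 at 12-hourly. In cohort 1, a draw at exactly 48 h or 96 h coincides with dose 9 or dose 17. If taken before that dose, it is 6 h after the previous one, which is 360/8 = 45 to 360/5 = 72 half-lives.

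**Step 2: length of the informative period.** Time to 10% of peak is log2(10) × half-life = 3.32 × 5 = 16.6 min to 3.32 × 8 = 26.6 min.

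**Step 3: chance that an untimed sample is informative.** This is (minutes of continued absorption + step 2) / dose interval.

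| Dose interval | Rapid (0 min) | 60 min (assumed) | 120 min (assumed) |
|---|---|---|---|
| 6 h | 4.6–7.4% | 21.3–24.0% | 37.9–40.7% |
| 8 h | 3.5–5.5% | 16.0–18.0% | 28.5–30.5% |
| 12 h | 2.3–3.7% | 10.6–12.0% | 19.0–20.4% |

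For example, 16.6/360 = 4.6% and (120 + 26.6)/360 = 40.7%.

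**Step 4: effect on a median of 9.** Take a looser criterion of five half-lives (3.1% remaining) and 0–60 min of nebulisation. At 6-hourly dosing the chance per sample is 25/360 = 6.9% to 100/360 = 27.8%. The binomial chance that at least 5 of 9 samples are informative, so that they govern the median, is 0.02% to 7.4%.

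**Step 5: slow absorption.** With first-order absorption in a one-compartment model at steady state, the trough as a percentage of the peak is:

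| Absorption half-life (assumed) | 6 h interval | 8 h interval | 12 h interval |
|---|---|---|---|
| 60 min | 2.1–2.5% | 0.5–0.6% | 0.03–0.04% |
| 120 min | 14.9–16.1% | 7.5–8.1% | 1.9–2.0% |
| 240 min | 38.8–40.5% | 27.6–28.8% | 13.8–14.5% |

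At 6-hourly dosing, an absorption half-life of about 2 h or more would leave a signal even in a trough sample. At 8- and 12-hourly dosing it would have to be longer than 2 h to pass the same 10% mark.

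**The case against.** The strongest reply is that section 2.6 calls absorption slow. Plasma tPA would then follow the absorption rate rather than the 5–8 min half-life, and step 5 shows that untimed samples could be informative. This stands as a possibility. But no rate is given, and slow absorption is one of the things these samples would have to show.

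The second reply is that other evidence agrees. Plasminogen and alpha-2 antiplasmin come from the same samples. Fibrinogen, which 2.6 treats as a measure of the rtPA absorbed, was tested at least daily in cohort 1 and did not fall (2.7.3). This also stands: the half-life of circulating tPA should not be applied to these markers or to tPA-PAI-1 complexes, and the documents give no half-lives for them. They are indirect, however, and speak to sustained activation. They are also thin: n falls from 9 to 2 by day 13, and the 10th percentile of plasminogen goes from 63.5 at baseline to 36.2 on day 3.

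A reader might infer four stronger things, which the documents do not support:

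- **That a negative tPA result was a foregone conclusion.** Day 3 and day 5 supply 9 + 8 = 17 samples. If they are independent, the chance of at least one informative sample is 1 − (1 − 0.046)^17 = 55% to 1 − (1 − 0.074)^17 = 73% with rapid absorption, and 98–99% with 60 min of continued absorption. Such values need not move a median but could show in the reported 10–90% ranges.
- **That most samples miss whatever the absorption.** With 180 min of continued absorption, (180 + 16.6)/360 to (180 + 26.6)/360 = 55–57% would be informative at 6-hourly dosing.
- **That cohort 2 was justified by tPA antigen.** Section 2.5 cites fibrinogen and plasminogen. The stopping and discontinuation rules (7.10, 7.3.3) use bleeding and fibrinogen among their criteria, never tPA antigen.
- **That the rat result shows absorption at the trial dose.** The rats received 1.25 mg/kg repeatedly; 10 mg is about 0.14 mg/kg at an assumed 70 kg.

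Finally, a laboratory manual might fix the draw times. None is among the documents, and section 7.5.1 does not refer to one.

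**Conclusion.** The point holds in a limited form. Untimed tPA antigen cannot by itself support the absorption half of the 2.7.4 statement. With rapid absorption, about 5–7% of samples would be informative at 6-hourly dosing, 3.5–5.5% at 8-hourly and 2–4% at 12-hourly. With 60–120 min of continued absorption, the 6-hourly figure is 21–41%. These figures rest on the protocol's half-life, the 10% threshold and random draw times. They do not apply if absorption is very slow, and the documents do not settle which case is true. The remaining markers support no evidence of sustained systemic fibrinolytic activation, and no more than that.

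The consequence is modest. The markers are exploratory, the cohort 1 data are labelled preliminary, and no trial rule depends on tPA antigen.

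**What to change.** 1. **Sampling.** In 7.5.1 and Appendix 1 footnote c, keep the number of samples. Take one of the 48 h and 96 h draws at the end of a nebulisation or within about 15 min of it, and the other just before a dose. At 15 min, 2^(−15/5) = 12.5% to 2^(−15/8) = 27% of the peak remains; by 30 min it is 1.6–7.4%, so a later window would lose most of the gain. The existing windows already contain several doses. The Appendix 1 column head (24 and 48 hours) disagrees with 7.5.1 and footnote c (48 and 96 hours) and can be reconciled in the same edit.
2. **Recording and analysis.** For every research sample, record the end time of the preceding nebulisation and the sample time. Derive these for cohort 1 where records allow. In the separate cohort 2 SAP, summarise tPA antigen and tPA-PAI-1 complexes by time since dose; the existing SAP lists the exploratory endpoints (5.3) but section 6 gives no analysis for them.
3. **Wording.** Limit the 2.7.4 statement to no evidence of sustained systemic fibrinolytic activation, unless the derived times show that the tPA antigen samples were informative.

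The cost is protocol wording, two time fields and some record review, with no extra samples. The downside is that two draws per patient may no longer coincide with routine bloods.

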## 2.5 Dosing schedule of rtPA for cohort 2 – rationale

During the first surge 9 patients were recruited to the pilot study, with 6 patients receiving IMV and 3 patients receiving non-invasive oxygen support. When the first surge died out, recruitment was not feasible and following discussion with DMC and TMG cohort 1 was closed for further recruitment and historical controls were recruited for evaluation of efficacy to enable a sample size calculation for a larger phase 3 study.

None of the bleeding events were considered related to the tPA. See preliminary safety data for cohort 1 in section 2.7. Final analysis of data is awaited; preliminary review of data is described here.

Preliminary data from the 9 patients from cohort 1 indicated a potential increase in arterial oxygen saturation levels, and importantly no evidence of consumption of fibrinogen nor a decrease in plasminogen levels was observed unlike the changes associated with intravenous administration.

Protocol v8.0 has been prepared at the start of the second UK surge. 30 patients will be recruited to this second cohort, with a minimum recruitment of 10 IMV patients and minimum of 10 patients receiving non-invasive ventilation. Early initiation of treatment appears to more effective, and this may be related either to lower fibrin burden or higher amount of plasminogen from the plasma exudate the substrate for rtPA. In the NIV and standard oxygen therapy group, a loading dose of 20 mg three times a day for 2 days followed by 20 mg twice a day is reasonable as intermittent fibrinolysis is effective. The loading dose potentially can help overcome the accumulation of PAI-1 early in the disease process, and is strong inhibitor of fibrinolysis.

The effect on arterial oxygen saturation levels appears to be less in IMV patients and drug losses can be expected because of the dead space created by the ventilator circuit. To account for this, we propose 20 mg every 8 hrs in patients receiving IMV.

Although the pilot study has used nebulisation every 6hrs, it is very reasonable to decrease the frequency to either twice a day for the non-invasive oxygen support group, or three times a day for the IMV group. The less frequent administration should make it easier for delivery teams.

The maximum duration of treatment will continue to be 14 days with a provision for early termination as described in section 7.3.3.

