In total, 7 bleeding events were identified. A bleed was considered not related to alteplase if the event happened 30 hrs after the last dose of treatment, alteplase exposure time period. Six of the seven bleeds were beyond alteplase exposure time period, and one was within the time period.

One bleed each met the criteria for ISTH major and minor bleed. Five bleeds did not meet the ISTH criteria for minor or major bleeds. The severity of bleeds as assessed for adverse event reporting resulted in five bleeds being categorised as mild and two events as moderate.

The severity assessment as used for AE reporting was used to further describe the bleeds.

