### 8.3.2 Causality

The assessment of relationship of adverse events to the administration of IMP is a clinical decision based on all available information at the time of the completion of the case report form.

The following categories will be used to define the causality of the adverse event:

Category	Definition

Related	A causal relationship between an IMP/investigational treatment and an adverse event is at least a reasonable possibility, i.e., the relationship cannot be ruled out.
Not related	There is no reasonable possibility of a causal relationship between an IMP/investigational treatment and an adverse event.

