## 8.4 Procedures for recording and reporting Serious Adverse Reactions

All SAEs will be recorded in the medical records in the first instance. Only serious adverse events assessed as likely to be related to IMP administration, Serious Adverse Reactions (SARs), will be recorded in the CRF, and the sponsor's SAE log. The SAE log will be reported to the sponsor at the end of the study.

SARs will be recorded from the start of treatment until the end of the study.

All SARs must be recorded on a SAE Reporting Form. The CI/PI or designated individual will complete the sponsor's SAE form and email to the Sponsor at [contact] immediately and no later than 24 hours of his / her becoming aware of the event. The Chief or Principal Investigator will respond to any SAE queries raised by the sponsor as soon as possible.

Completed SAE forms must be sent within 24 hours of becoming aware of the event to the Sponsor

Email forms to [contact]

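### Section 2.7 classes cohort 1 bleeds as unrelated by a 30 h cut-off that is absent from the causality method in 8.3.2, and six of the seven bleeds meet it

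*Protocol*

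**What the plan says.** Protocol section 2.7 reports preliminary safety data for the nine patients treated in cohort 1: "In total, 7 bleeding events were identified". It gives a time rule for causality, "A bleed was considered not related to alteplase if the event happened 30 hrs after the last dose of treatment", and the split that follows from it: "Six of the seven bleeds were beyond alteplase exposure time period, and one was within the time period". On severity it reports: "One bleed each met the criteria for ISTH major and minor bleed". Section 2.5, which sets out the reasons for the cohort 2 schedule, adds: "None of the bleeding events were considered related to the tPA".

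The general method is in section 8.3.2: "The assessment of relationship of adverse events to the administration of IMP is a clinical decision based on all available information". There an event is related if a causal link is at least reasonably possible, and unrelated only if there is no such possibility. No time limit appears. Section 8.4 adds: "SARs will be recorded from the start of treatment until the end of the study".

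The 30 h window does appear in section 7.10, where it limits which bleeds can trigger a trial stop. The SAP does not mention it. The first primary safety endpoint (protocol 10.1.2, repeated in the SAP study summary) is limited to major bleeds attributed to the drug. SAP 5.1 lists major bleeds without that limit.

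**The concern.** The documents contain two ways of deciding whether a bleed was caused by alteplase. One is a judgement on each event, with the benefit of doubt going to relatedness. The other is a cut-off whose only possible result is unrelated. For the same events, the cut-off can lower the related count or leave it unchanged, but it cannot raise it.

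This matters because attribution decides what counts towards a primary safety endpoint. It also decides which serious events go on the SAE form (8.4). The result of no related bleeds is already stated in section 2.5. A reader of that statement should know which method produced it.

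**Working it through.** **Inputs**
- Treated patients in cohort 1: 9 (2.7: "Preliminary data from the 9 treatment arm patients is summarised below").
- Bleeds: 7; beyond 30 h: 6; within: 1 (2.7).
- ISTH class: 1 major, 1 minor, 5 neither (2.7).
- Adverse-event severity: 5 mild, 2 moderate (2.7).
- Bleeds considered related: 0 (2.5).

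**Step 1: the plan's own counts.** Timing: 6 + 1 = 7. ISTH class: 1 + 1 + 5 = 7. Severity: 5 + 2 = 7. All three splits agree with the stated total.

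**Step 2: reach of the time rule.** 6/7 = 85.7% of bleeds meet it, and 1/7 = 14.3% does not.

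**Step 3: the rules side by side**

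| Place | Purpose | Time limit |
|---|---|---|
| 2.7 | Causality of cohort 1 bleeds | 30 h after last dose |
| 8.3.2 | Causality of all adverse events | None |
| 7.10 | Bleeds that can stop the trial | 30 h after last dose |
| 10.1.2, item 1 | Endpoint: attributable major bleeds | None |
| 10.6.2 and SAP 6.3 | Summary of bleeding by group | None, and no relatedness filter |

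Section 2.7 uses for causality a window that the current procedures define only for stopping. Its rule is not part of the method in 8.3.2.

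**Step 4: what could change**
- All bleeds. No related count under 8.3.2 can be computed, because the available text gives no event-level assessments. The logical limits are 0 and 7, and the cut-off could account for at most 6 of those. These are limits, not estimates.
- Primary endpoint. It counts major bleeds only, and one bleed was ISTH major. With none considered related, the attributable major count is 0. Under 8.3.2 it could be 0 or 1, a change of at most one event. The text does not say on which side of 30 h the major bleed fell. If it was inside the window, the time rule had no effect on this endpoint.

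**Step 5: scale in nine patients.** The exact two-sided 95% upper limit for 0 of 9 is 1 − 0.025^(1/9) = 33.6%. For 1 of 9 (11.1%) the exact interval is 0.3% to 48.2%. Neither count excludes a substantial risk, so moving one event would change the statement made more than the evidence.

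**The case against.** A fair defence has four parts.

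1. **The window has a pharmacological reason.** Section 2.7 presents it as the period of exposure. Section 2.6 gives a circulating half-life of 5 to 8 minutes, so 30 h is at least 30 × 60 / 8 = 225 half-lives. Sections 2.7.3 and 2.7.4 report no fall in fibrinogen and no sign of significant absorption. An assessor under 8.3.2 could reasonably use these facts to find no link. This stands as a reason to weigh time heavily, but it does not make the cut-off part of 8.3.2.

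2. **Causality was evaluated.** Section 2.7 says every bleed was evaluated for severity and causality. The text before 2.7.3 is incomplete in the copy reviewed and may hold event-level assessments. A reader might infer that six bleeds were removed from the related count by the clock alone. The documents do not support that: nothing shows that any of the six would otherwise have been judged related. The seventh bleed, inside the window, was also considered unrelated, so the cut-off does not explain the whole result.

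3. **Planned reporting limits the harm.** The data in 2.7 are labelled preliminary. Protocol 10.6.2 and SAP 6.3 summarise bleeding events whatever their attribution, and 7.7.3 records the date and time of onset. This stands and keeps the point modest.

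4. **Two tempting supports are weak.** The recording period in 8.4 and the 48 h fibrinogen window in 10.1.2 set how long data are collected. They are not causality rules and do not show that 30 h is wrong.

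Two further inferences also go too far. Nothing applies the 30 h causality rule to cohort 2, where 8.3.2 governs as written. The reasons section 2.5 gives for the cohort 2 schedule are inhibitor load, circuit losses, intermittent fibrinolysis and ease of delivery. The sentence on bleeds is safety background there.

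**Conclusion.** The conflict is real and limited. Section 2.7 states a fixed 30 h rule for causality that 8.3.2 does not contain, and six of seven cohort 1 bleeds (86%) meet it. The rule can act in only one direction. Whether it changed any classification cannot be determined from the available text. The attributable-major-bleed endpoint could change by at most one event in cohort 1.

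This rests on three assumptions: that the time rule means onset later than 30 h after the last dose, that the preliminary ISTH classes hold in the final data, and that 8.3.2 is the protocol's intended method for bleeds as for other adverse events. It is worth correcting before the final cohort 1 analysis. It does not show that any bleed was caused by the drug.

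**What to change.** - **Protocol 2.7 and 8.3.2:** reconcile the two. If case-by-case assessments already exist, cite them and reword 2.7 so that the 30 h window is described as one consideration.
- **Final cohort 1 analysis:** confirm or redo the 8.3.2 assessment of all seven bleeds. Use time since last dose as one input and not as an automatic cut-off. Correct the statement in 2.5 if the result changes.
- **Protocol 10.6.2, SAP 6.3 and the separate cohort 2 SAP:** state that attribution for the primary bleeding endpoint follows 8.3.2. List every bleed with hours from the last dose, causality result and ISTH class. Keep the summary of all bleeds regardless of attribution.

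The cost is the reassessment of seven events and one derived column, since onset times are already collected. The related count may become less favourable.
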